19 DATA CONTROLLER

Guy's and St Thomas' NHS Foundation Trust is the Data Controller as defined by UK general data protection legislation (UK GDPR) for this study and as such agrees to comply with the obligations placed on a Data Controller by the UK GDPR. This is not limited to, but includes, being responsible for and able to demonstrate compliance with the principles relating to Processing of Personal Data (Article 5 UK GDPR).

20 REPORTING AND DISSEMINATION

The results from this study will be presented at AI, radiology, and emergency medicine meetings, and published in high-impact peer-reviewed journals in collaboration with all investigators.

Useful reading/websites

Integrated Research Application System (IRAS)

<https://www.myresearchproject.org.uk/>

Health Research Authority (HRA)

www.hra.nhs.uk

HRA Guidance for Patient Information Sheet and Informed Consent

<http://www.hra.nhs.uk/research-community/before-you-apply/participant-information-sheets-and-informed-consent/>

CONSORT statement ICH Harmonised Tripartite Guidelines for Good Clinical Practice (1996)

http://www.ich.org/fileadmin/Public_Web_Site/ICH_Products/Guidelines/Efficacy/E6/E6_R1_Guideline.pdf

Martin Bland et al, Statistical guide for research grant applications

<http://www-users.york.ac.uk/~mb55/guide/guide.htm>

Includes detailed information and definitions of many aspects required for a research protocol.

Declaration of Helsinki

<http://www.wma.net/en/30publications/10policies/b3/index.html>

[figure not shown]

| Urgent Safety Measures | Chief Investigator | Contact the Sponsor and MREC Immediately Within 3 days | By phone Substantial amendment form giving notice in writing setting out the reasons for the urgent safety measures and the plan for future action. | Main REC and Sponsor Main REC with a copy also sent to the sponsor. The MREC will acknowledge this within 30 days of receipt. |
| Progress Reports | Chief Investigator | Annually (starting 12 months after the date of favourable opinion) | Annual Progress Report Form (non-CTIMPs) available from the NRES website | Main REC with a copy to be sent to the Sponsor |
| Declaration of the conclusion or early termination of the study | Chief Investigator | Within 90 days (conclusion) Within 15 days (early termination) The end of study should be defined in the protocol | End of Study Declaration form available from the NRES website | Main REC with a copy to be sent to the sponsor |
| Summary of final Report | Chief Investigator | Within one year of conclusion of the Research | No Standard Format However, the following Information should be included: Where the study has met its objectives, the main findings and arrangements for publication or dissemination including feedback to participants | Main REC with a copy to be sent to the sponsor |

APPENDIX 4

Study Flowchart

APPENDIX 5

Data Dictionary

5.1. Summary

A data dictionary of a study explains exactly what data will be collected by each site and in what format. It explains the record type level (e.g., pre-scan, scan, post-scan, etc.) and attribute level (e.g., patient identifier, age, sex, date of referral, etc.) requirements. It can only be produced after an analysis of the data available at each site, to ensure study-wide consistency.

It will incorporate the following:

- Cohort and data selection criteria
- Source data format
- Data schema (record types along with their attributes, attribute formats, attribute capture requirement and attribute description)

5.2 Cohort and data selection criteria

A common set of cohort and data selection criteria will be developed once the study team has selected the sites and discussed the detailed format and content of their clinical records. The data in each site is likely to differ, especially across regional boundaries (e.g., CDS datasets in England versus SMR datasets in Scotland). The existing clinical protocols are also likely to differ between sites, which influences the way in which data is sequenced, modelled, and stored.

5.3 Source data format

Each site will provide a single file for each record, once every three months (to be defined in consultation with each site). Each file will be in CSV format, with a fixed number of commas separated values, each pertaining to an attribute as defined within the schema for that record type.

The naming convention will be:

<Site ID>_<Batch ID>_<dataset short name>_<version number>.csv

Where:

- 'Site ID' is the number allocated to as site by the study team
- 'Batch ID' is the sequential number indicating the 3-monthly batch that the file relates to (e.g., the first batch is 1, after 3 months the next batch is 2, etc.)
- 'Dataset short name' is the short name for the dataset within the file (e.g., 'patientcore', 'referrals', 'labresults', etc.)
- 'Version number' is used where the same data needs to be sent more than once, perhaps because of quality issues in the previous file. It increments each time a new version of a file is sent.

An example record format for patient demography might be as follows:

<Patient identifier, postcode sector, age, sex, ethnicity>

98740833,ML5 2,63,male,1A

89837748,AB43 6,27,female,5B

The exception will be AI results files and ground truth records, which will be linked and returned as individual json format files within compressed folders. These folders will be named as follows:

<Site ID>_<Batch ID>_<dataset short name>_<version number>.zip

Where:

'Site ID' is the number allocated to a site by the study team

'Batch ID' is the sequential number indicating the 3-monthly batch that the file relates to (e.g., the first batch is 1, after 3 months the next batch is 2, etc.)

'Dataset short name' is the short name for the datasets within the file. It will be 'airesults' for the AI results files and 'gtresults' for the ground truth results files.

'Version number' is used where the same data needs to be sent more than once, perhaps because of quality issues in the previous file. It increments each time a new version of a file is sent.

5.4 Schema

The following record types are to be extracted from routinely collected clinical data or data that is made readily available through the qER platform or from clinical fellow's report after he/she reviews the NHS trust radiology reports.

- Pre-scan
- Scan
- Post-scan
- Ground truth

Limitations of documented schema

- The list of attributes in each of the record types is not a comprehensive list. Additional attributes for study analysis may be **derived** from attributes listed below for each of the four record types during the study analysis phase of the study as applicable.
- The record types and attributes listed below are not the same as short datasets. A subset of attributes within each record type or a combination of attributes between multiple record types may constitute a short dataset depending on the feasibility of data capture. All record types will have one or more unique identifiers which can be used to merge multiple record types or multiple short datasets.

5.4.1 Pre-scan

This record type contains all attributes that are collected before a Head NCCT scan is completed for the patient in the study

| | Attribute | Data type | Mandatory | Description | Source |
|---|-----------------|-----------|-----------|---------------------------------------|----------|
| 1 | Site identifier | Varchar | Yes | The identifier allocated by the study | Assigned |

| | | | | | |
|----|--|---------------------------------|-----|--|--|
| | | | | team to the site which this patient belongs. | |
| 2 | Study patient identifier | Varchar | Yes | Unique Identification number given to each patient whose data is being analysed for the study. | Assigned |
| 3 | Patient identifier | Varchar | Yes | Unique identifies for a patient (across all sites) - likely to be conflation of site ID and site patient ID. | Assigned |
| 4 | Cohort | Varchar | Yes | The reason for having this patient in the cohort | Assigned |
| 5 | Date of Birth (DOB) | Date dd.mm.yyyy | Yes | This will determine the age of patient at time of scan | DICOM Meta Data |
| 6 | Ethnicity | Varchar | No | The likely race/ethnicity based on self-reported sources, public sources and surname/ethnicity tables. | Site specific electronic patient record |
| 7 | Gender | Numeric | Yes | Gender of the patient | DICOM Meta Data |
| 8 | Time of arrival to Emergency Department (ED) | Datetime dd.mm.yyyy hh:mm | Yes | The time of patient arrival to the Emergency Department. | Site specific electronic patient record |
| 9 | Time of triage in ED | Datetime dd.mm.yyyy hh:mm | Yes | The time of first digitally recorded clinical contact. | Site specific electronic patient record |
| 10 | Initial location cared for | Varchar | No | Where the patient was first seen. | Site specific electronic |

| | | | | | |
|--------|---|---------------------------------|-----|---|------------------------------------|
| | | | | | patient record |
| 1 1 | Indication for Head CT | Varchar | No | What did the patient present with? List 1 - Trauma; 2 - Altered focal neurology; 3 - Reduced GCS; 4 - Headache; 5 - Seizures; 6 - Other | Radiology Report. RIS - free text. |
| 1 2 | Time of CT Request | Datetime dd.mm.yyyy hh:mm | Yes | Time the clinical team requested the patient to have a head CT scan. | RIS |
| 1 3 | Does NCCT head meet qER inclusion and exclusion criteria? | Binary | Yes | Technical requirements of qER read met. | DICOM Meta Data, qER Log |
| 1 4 | CT Scan Model | Varchar | No | The model of the scanner used to generate images. | DICOM tag |
| 1 5 | CT Scan Manufacturer | Varchar | No | The manufacturer of the scanner uses to generate images. | DICOM tag |
| 1 6 | CT Scan Software Version | Varchar | No | Software version of the CT scan. | DICOM Meta Data |

5.4.2 Scan

This record type contains all attributes that are collected during the time when a patient is undergoing a Head NCCT scan and immediately after it to capture the necessary data elements for study analysis. For attributes which are of 'binary' data types, a value of 1 will indicate the presence of that attribute and 0 indicates absence.

| | Attribute | Data type | Mandatory | Description | Source |
|---|--------------------|-----------|-----------|---|----------|
| 1 | Patient identifier | Varchar | Yes | Unique identifies for a patient (across all sites) - likely to be | Assigned |

| | | | | | |
|----|--------------------------------|---------------------------------|-----|---|------------------------|
| | | | | conflation of site ID and site patient ID. | |
| 2 | SOP instance UID | Varchar | Yes | The unique ID for the image to which the report relates | DICOM Meta Data |
| 3 | Accession number | Varchar | Yes | Unique identifier linking the report to a suite of imaging studies | DICOM Meta Data |
| 4 | Time of CT Scan Acquisition | Datetime dd.mm.yyyy hh:mm | Yes | The time at which CT scan was completed for the patient | DICOM Meta Data |
| 5 | Out of hours scans? | Binary | Yes | Whether the scan was sent for teleradiology reporting (value = 1) or not (value = 0) | qER log/RIS/PACS |
| 6 | Time NCCT Brain was received | Datetime dd.mm.yyyy hh:mm | Yes | The time NCCT was received by qER | qER Log |
| 7 | Was CT image processed by qER? | Binary | Yes | Did the image meet qER requirements for processing? | qER Log |
| 8 | Time qER report received | Datetime dd.mm.yyyy hh:mm | Yes | The time the qER report left the gateway and available for the radiologists to review | qER Log |
| 9 | qER probability score for ICH | Numeric | Yes | Probability of the presence of intracranial haemorrhage | qER Log |
| 10 | qER ICH | Numeric | Yes | Presence or absence of ICH | qER Log/ qER Report |
| 11 | qER probability score for EDH | Numeric | Yes | Probability of the presence of extradural haemorrhage | qER Log |

| | | | | | |
|----|---------------------------------------|---------|-----|---|------------------------|
| 12 | qER EDH | Binary | Yes | Presence or absence of EDA | qER Log |
| 13 | qER probability score for SDH | Numeric | Yes | Probability of the presence of subdural haemorrhage | qER Log |
| 14 | qER SDH | Binary | Yes | Presence or absence of SDH | qER Log |
| 15 | qER probability score for SAH | Numeric | Yes | Probability of the presence of subarachnoid haemorrhage | qER Log |
| 16 | qER SAH | Binary | Yes | Presence or absence of SAH | qER Log |
| 17 | qER probability score for IPH | Numeric | Yes | Probability of the presence of intraparenchymal haemorrhage | qER Log |
| 18 | qER IPH | Binary | Yes | Presence or absence of IPH | qER Log |
| 19 | qER probability score for IVH | Numeric | Yes | Probability of the presence of intraventricular haemorrhage | qER Log |
| 20 | qER IVH | Binary | Yes | Presence or absence of IVH | qER Log |
| 21 | qER probability score for MS | Numeric | Yes | Probability of the presence of midline shift | qER Log |
| 22 | qER MS | Binary | Yes | Presence or absence of midline shift | qER Log/ qER Report |
| 23 | qER probability score for mass effect | Numeric | Yes | Probability of the presence of mass effect | qER Log |
| 24 | qER ME | Binary | Yes | Presence or absence of mass effect | qER Log/ qER Report |

| | | | | | |
|----|--|---------------------------------|-----|---|----------------------------------|
| 25 | qER probability score for cranial fracture | Numeric | Yes | Probability of the presence of cranial fracture | qER Log |
| 26 | qER fracture | Binary | Yes | Presence or absence of cranial fracture | qER Log/ qER Report |
| 27 | qER probability score for atrophy | Numeric | Yes | Probability of the presence of atrophy | qER Log |
| 28 | qER atrophy | Binary | Yes | Presence or absence of atrophy | qER Log/ qER Report |
| 29 | qER probability score for infarct | Numeric | Yes | Probability of the presence of hypodensities suggestive of infarct | qER Log |
| 30 | qER Infarct | Binary | Yes | Presence or absence of hypodensities suggestive of infarct | qER Log/ qER Report |
| 31 | Time CT Report Generated by radiologist | Datetime dd.mm.yyyy hh:mm | Yes | The time when the final CT report was generated by a radiologist. | RIS/ PACs |
| 32 | qER full report of NCCT Brain | Varchar | Yes | Published final qER report | qER log/RIS/PA CS |
| 33 | qER Scan Category | Integer | Yes | Prioritised or No Finding or Other non-prioritised finding? 1= Prioritised 2 = No finding 3 = Other non-prioritised finding 4 = Not processed | Derived from qER Log/ qER Report |

5.4.3 Post-scan

This record type will capture attributes that have occurred after the NHS radiologist final report was available for stakeholders to review including any patient follow-up data that is collected. For

attributes which are of 'binary' data types, a value of 1 will indicate the presence of that attribute and 0 indicates absence.

| | Attribute | Data type | Mandatory | Description | Source |
|---|--------------------|-----------|-----------|--|--------------------------|
| 1 | Patient identifier | Varchar | Yes | Unique identifies for a patient (across all sites) - likely to be conflation of site ID and site patient ID. | Assigned |
| 2 | SOP instance UID | Varchar | Yes | The unique ID for the image to which the report relates | DICOM Meta Data |
| 3 | Accession number | Varchar | Yes | Unique identifier linking the report to a suite of imaging studies | DICOM Meta Data |
| 4 | Rad ICH | Binary | Yes | Radiologist reported presence of Intracranial haemorrhage in the radiology report? | Clinical fellow's report |
| 5 | Rad MS | Binary | Yes | Radiologist reported presence midline shift in the radiology report? | Clinical fellow's report |
| 6 | Rad ME | Binary | Yes | Radiologist reported presence mass effect in the radiology report? | Clinical fellow's report |
| 7 | Rad Fracture | Binary | Yes | Radiologist reported presence cranial/skull fracture in the radiology report? | Clinical fellow's report |
| 8 | Rad Atrophy | Binary | Yes | Radiologist reported presence atrophy in the radiology report? | Clinical fellow's report |

| | | | | | |
|----|--|-------------------------------------|-----|--|--|
| 9 | Rad Infarct | Binary | Yes | Radiologist reported presence hypodensities suggestive of infarct in the radiology report? | Clinical fellow's report |
| 10 | Rad Other | Binary | Yes | Radiologist reported presence of any other findings other than the six target abnormalities in the radiology report? | Clinical fellow's report |
| 11 | Rad Scan Category | Integer | Yes | Prioritised or No Finding or Other non-prioritised finding? 1= Prioritised 2 = No finding 3 = Other non-prioritised finding | Derived from clinical fellow's report |
| 12 | Discordance between qER report and NHS Trust radiologist report | Binary | Yes | Is there a discordance between qER report findings and NHS Trust radiologist report? 1 = Yes 0 = No | Derived from clinical fellow's report and qER report |
| 13 | Discordance Review Decision: Which AI findings were accepted by the panel? | Varchar | Yes | To capture the agreement between qER and trust radiologist based on specific findings. | Derived from clinical fellow's report and qER report |
| 14 | Time of treatment related to head CT findings in ED | Datetime dd.mm.yyyy hh:mm | No | Time of intervention to treat CT Head findings. | Site specific electronic patient record |

| | | | | | |
|----|--|-------------------------------------|-----|---|---|
| | | | | | |
| 15 | Time of first intervention for critically identified scans | Datetime dd.mm.yyyy hh:mm | No | Time recorded for initial treatment option and/or referral. | Site specific electronic patient record |
| 16 | Time of discharge or referral | Datetime dd.mm.yyyy hh:mm | Yes | Electronic discharge point from ED (to ward or home). | Site specific electronic patient record |
| 17 | Length of stay in hospital | Numeric | Yes | Length of stay in hospital related to that admission. | Site specific electronic patient record |
| 18 | Was the patient enrolled in other clinical trial? | Binary | Yes | Has the patient been recruited to another study? 1 = Yes 0 = No | Site specific electronic patient record |
| 19 | If 21 = Yes; Clinical trial number [PLACEHOLDER] | Clinical trial code | Yes | The study ID if the patient is a subject? | Site specific electronic patient record |
| 20 | Patient's National Data Opt Out | Binary | Yes | If patient has selected National Data Opt out, their data will be excluded from final analysis. 1= Patient data excluded from analysis 0 = Not excluded | |

| | | | | | |
|----|--|------------------------|-----|--|---|
| | | | | | |
| 21 | Death within 28 days following discharge | Binary | Yes | Had the patient died within 28 days following discharge from NHS Trust hospital? 1 = Yes 0 = No | Site specific electronic patient record |
| 22 | Date of Death | Date dd.mm.yyyy | Yes | If the patient had died within 28 days following discharge from NHS Trust hospital, what is the date of death | Site specific electronic patient record |
| 23 | Immediate condition | Varchar | Yes | ICD code relating to the disease or condition directly relating to death | Site specific electronic patient record |
| 24 | Contributing condition | Varchar | No | ICD code relating to other significant conditions contributing to the death but not related to the disease or condition causing it | Site specific electronic patient record |

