6.3 Secondary Outcome Measures

Utility of qER compared to standard of care:

- Time taken from acquisition to report NCCT head for patients without prioritised findings in Emergency Department
- Time taken from acquisition to report completed for patients with absence of findings on NCCT head scans in Emergency Department
- To assess impact of qER on radiology reporting workflow on other requests for CT scans
- To assess impact of teleradiology on qER supported reporting
- Time to diagnosis from CT acquisition.
- Time to referral from CT acquisition.
- Time to initiation of treatment from CT acquisition for prioritised scans.
- Death within 28 days of NCCT head acquisition
- Percentage of NCCT heads that qER classifies as prioritised and absence of findings.
- Percentage of qER non prioritised scans that radiologist identified as having prioritised finding
- Percentage of qER non prioritised but identified by radiologist as absence of finding.

Technical Evaluation of product performance:

- Sensitivity, specificity, positive and negative predictive values of qER in detecting scans with prioritized findings overall and also stratified by all 6 target abnormalities.
- Percentage of CT scans that could not be processed by qER due to technical factors.

Safety of qER:

- To assess the safety of qER of identifying patients with no prioritised findings identified on NCCT head.
- Percentage of patient NCCT Head reported incorrectly as qER non prioritised.
- Time from acquisition to reporting of CT Chest Abdo Pelvis (CAP) and Pulmonary Angiograms (CTPA) within the trust.

Health economic assessment:

- Compare costs and health benefits between pre and post implementation of qER, including cost evaluation of fully automatic diagnosis of high confidence normal triage.

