6.6 Ground Truth

Both the prospective (stepped wedge) and retrospective (technical evaluation) elements of this study compare the performance of qER against ground truth and

ground truthing is required for confirming which scans contain a prioritised finding and not.

The following **prospective** scenarios (i.e. from the stepped-wedge study) will require independent generation of ground truth by two post-fellowship radiologists (and an arbitrating senior radiologist, where there is interobserver disagreement):

- All images where radiologist disagrees with the qER assessment.

Head-NCCT scans where original reporting radiologist agreed with Qer assessment will not be sent for ground truthing and the original report will be considered as the ground truth for such scans.

All NCCT head images will be reviewed by trust radiologist. Those that the trust radiologist disagrees will require independent generation of ground truth by two post-fellowship radiologists (and an arbitrating senior radiologist, where there is interobserver disagreement).

An image will be presented to ground truth radiologists only after the result has been generated by qER. Images from all sources will be presented in a single list for ground truth generation, so that radiologists cannot identify the source (i.e., whether the ground truth is necessary because there was a discrepancy, or not). All images will be deidentified to ensure the radiologist cannot identify the patient and thereby view the corresponding AI result or seek additional supporting clinical data to make a ground truth decision.

[figure not shown]

Figure 4: Ground truth for retrospective data.

[figure not shown]

Figure 5: Ground truth for prospective data.

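### Coding the radiologist's findings as 1/0 cannot separate an unmentioned atrophy or infarct from an excluded one, and that 0 then feeds the scan category, the discordance flag and the ground truth

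*Protocol*

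**What the plan says.** Protocol, Appendix 5, 5.4.3 Post-scan, makes each radiologist finding a mandatory binary field. For atrophy the field asks: "Radiologist reported presence atrophy in the radiology report". For infarct it asks: "Radiologist reported presence hypodensities suggestive of infarct in the radiology report". The rule for all binary fields there is that "a value of 1 will indicate the presence of that attribute and 0 indicates absence". No value exists for a report that does not mention the finding.

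The reporting radiologist fills in no per-finding form. Under 5.4 Schema the data come "from clinical fellow's report after he/she reviews the NHS trust radiology reports".

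Two further fields rest on this coding. Rad Scan Category (prioritised, no finding, other non-prioritised finding) is "Derived from clinical fellow's report". The binary discordance field asks: "Is there a discordance between qER report findings and NHS Trust radiologist report". Neither has a level for not stated, whereas qER Scan Category in 5.4.2 does have a fourth level, for scans not processed.

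Section 5.1 of the main text defines the qER non-prioritised findings as atrophy and hypodensities suggestive of infarct. Section 6.3 then lists as a utility outcome: "Percentage of qER non prioritised but identified by radiologist as absence of finding". It also asks for sensitivity, specificity and predictive values for each of the six abnormalities. Under section 6.6, scans on which radiologist and qER agree are not re-read, and "the original report will be considered as the ground truth for such scans".

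**The concern.** A routine emergency report may say nothing about atrophy or an old infarct. Under the rule above the fellow must still enter 0, and two things follow.

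- If qER has flagged atrophy or infarct, the silent report can be placed in the No finding category. It is then counted in section 6.3 as the radiologist having identified absence, which silence does not do.
- If qER has missed the finding, 0 meets 0. The scan is concordant and is not re-read on that account, so the report becomes the truth and the miss is scored as a true negative.

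At stake are one utility percentage and the prospective accuracy of two of the six abnormalities. For sensitivity and NPV the error favours the device. The true and false positive and negative counts are also inputs to the health economic analysis (section 6.5.3).

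**Working it through.** The protocol states no figure to reproduce on this point, so the field rules are traced first and then illustrated.

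**Tracing the rules for atrophy or infarct that is truly present**

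| qER | Report | Rad field | Discordant | Re-read | Scored as |
|---|---|---|---|---|---|
| positive | mentions | 1 | no | no | true positive |
| positive | silent | 0 | yes | yes | true positive if the panel confirms; still radiologist absence in 6.3 if nothing else is reported |
| negative | mentions | 1 | yes | yes | false negative |
| negative | silent | 0 | no | no | true negative (wrong) |

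The panel re-read in the second row does not repair the 6.3 outcome, because that outcome is defined on the radiologist's report.

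**Inputs, all assumed because the protocol gives none:** m = share of true findings that the report mentions, 0.9 to 0.3; true sensitivity s = 80% or 90%; specificity 90%; prevalence of atrophy or infarct 20% to 40%; correct panel reads; no other finding on the scan.

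**Apparent sensitivity** = s / (s + (1 − s)m). With s = 0.8 and m = 0.9 this is 0.8 / (0.8 + 0.18) = 81.6%. Only the mention rate among qER misses matters here, since silent qER-positive scans go to the panel.

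**Apparent NPV**, per 10,000 scans at prevalence 20%, s = 80%: qER-negative scans are 7,200 true negatives + 400 misses = 7,600, so the true NPV is 7,200 / 7,600 = 94.7%. As coded it is (7,200 + 400(1 − m)) / 7,600.

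**6.3 percentage** = (TP(1 − m) + FP) / (TP + FP). At prevalence 20% and s = 80%, TP = 1,600 and FP = 800, so m = 0.9 gives (160 + 800) / 2,400 = 40.0%. At prevalence 40% and s = 90%, TP = 3,600 and FP = 600, giving (360 + 600) / 4,200 = 22.9%. These two settings give the ends of the range below.

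| m | Sensitivity, true 80% | Sensitivity, true 90% | NPV, true 94.7% | 6.3 percentage |
|---|---|---|---|---|
| 1.0 | 80.0% | 90.0% | 94.7% | 14–33% |
| 0.9 | 81.6% | 90.9% | 95.3% | 23–40% |
| 0.7 | 85.1% | 92.8% | 96.3% | 40–53% |
| 0.5 | 88.9% | 94.7% | 97.4% | 57–67% |
| 0.3 | 93.0% | 96.8% | 98.4% | 74–80% |

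**Would dropping unmentioned qER-negative scans be enough?** No. Silent qER-positive scans are still panel-read, so the true positives stay at s and the false negatives at (1 − s)m. Sensitivity is again s / (s + (1 − s)m), the same column as above. Dropping silent true negatives would also lower apparent specificity.

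**Safeguards in the plan.** Section 6.1.1.3 sends a random 500 scans for ground truthing. That is 500 / 16,800 = 3.0% of the expected total, and a larger share of the aided-phase scans, since the total covers both phases. Expected hidden misses among them are 500 × prevalence × (1 − s) × (1 − m). For m = 0.9 to 0.5 this runs from 500 × 0.2 × 0.1 × 0.1 = 1 to 500 × 0.4 × 0.2 × 0.5 = 20.

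**The case against.** The strongest reply is that the field is right as written. It asks whether presence was reported, and 0 is the true answer for a silent report. This stands: the fault lies in how the 0 is used afterwards.

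A second reply is that the dictionary is unfinished. Section 8.3 calls it an example, 5.1 of Appendix 5 says it can be produced only after the site data have been analysed, and the derivation of Rad Scan Category is not spelled out. If a Rad Other finding moves a scan to category 3, fewer silent reports reach category 2. That is fair. However, 5.4 Schema allows further attributes to be derived only from those listed, and non-mention cannot be derived from a 0. The usual care report is collected, but recovering the distinction would mean coding it again.

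Third, there are safeguards: the random 500, and the retrospective 500 per site in section 6.4, stratified by target abnormality. They are real but partial. Nothing in the protocol uses them to correct the full-cohort figures, and section 6.6 and 5.4.4 of Appendix 5 describe prospective ground truth for discordant scans only, which conflicts with the random 500.

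Fourth, the illustration leans high. The panel records all six abnormalities, so a silent miss on a scan discordant for another reason is recovered. Category 2 also needs silence on both atrophy and infarct. Both points stand.

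A reader might infer that qER misses in general are hidden, or that the primary result is biased. The documents do not support either. The case rests on atrophy and infarct, which do not trigger prioritisation, while the primary outcome concerns scans with prioritised findings. The only link is indirect: section 15.2 adjusts the TAT model for ground-truth infarct, and that covariate could carry the same misclassification. A shift between phases in the group with absence of findings, because radiologists mention more once they see qER output, is possible but not shown.

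**Conclusion.** The point holds in limited form. Followed as written, the plan scores a qER miss of atrophy or infarct with a silent report as a true negative, unless the scan is re-read for another reason. It can also count a silent report on a qER atrophy or infarct call as the radiologist identifying absence. The direction for full-cohort prospective sensitivity and NPV is upward for any omission rate above zero.

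The size is unknown. The 82% to 93% against a true 80% rests on an assumed mention rate of 90% down to 30%, correct panel reads and no recovery through other discordances. The 6.3 ranges rest in addition on assumed prevalence, sensitivity and specificity. The m = 1.0 row is not a correct value for that outcome, which is defined on what radiologists identify rather than on truth. It shows only how much of the percentage non-mention could supply. This is worth correcting because it is fixed at data capture, but it concerns secondary outcomes.

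**What to change.** 1. Code Rad Atrophy and Rad Infarct as 1 = reported present, 0 = reported absent, 9 = not mentioned. State a coding rule under which a global normal statement counts as 0.
2. Give Rad Scan Category a separate level for scans with no finding coded 1 but atrophy or infarct coded 9. Reserving category 2 for scans with nothing coded 1 would not do, since it still admits silent reports.
3. Report the 6.3 percentage with and without the scans at that level, stating the denominator, and report the share of 9s by phase.
4. Do not treat 9 as agreement or as ground truth.
5. Take prospective sensitivity, specificity and predictive values for atrophy and infarct from the random 500 panel-read scans, or weight all panel-read scans by their sampling probability. Do not use the full cohort with only the qER-negative 9s dropped.
6. Reconcile section 6.1.1.3 with section 6.6 and with 5.4.4 of Appendix 5, so that the random 500 is clearly part of prospective ground truthing.

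The cost is slightly more coding in fields the fellow already fills, and wider intervals for two abnormalities. At the assumed prevalence of 20% to 40%, the 500 scans hold 100 to 200 positives. The 95% half-width at a sensitivity of 80% is then 1.96 × √(0.8 × 0.2 / 100) = 7.8 points down to 1.96 × √(0.8 × 0.2 / 200) = 5.5 points, and wider if either abnormality alone is rarer.
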